Design:	
Prospective, single center, randomized, single-blind, controlled, 2-arm parallel group trial in Milan, Italy (Pr. [name], Targeted Research Center)
 
The total duration of the study is expected to be 24 months with ~12 months of enrollment.
 
Approximately 80 subjects suffering from persistent AF will be randomized in a 1:1 fashion to the following investigation arms:
 
 - Modified circumferential pulmonary vein ablation alone (mCPVA); - Substrate-targeted ablation guided by AF substrate mapping, followed by completion of modified circumferential pulmonary vein ablation (Substrate+ mCPVA) 
 • Ablate the areas that have fast and regular electrical activities, starting from the fastest cycle length (defined by Mean CL in the range of 120-250 milliseconds, and SD CL in the range of 1-30 milliseconds) • Ablate the areas that have consistent rotational or focal propagation pattern (defined by conduction velocity vectors) • Ablate the areas that comprises the slow conduction zone of possible arrhythmia circuits • If AF terminates during RF ablation, stimulation protocol will be used to examine if AF is re-inducible. If AF is re-inducible and physician decides to remap, mapping will be performed again for substrate-targeted ablation. If AF is not re-inducible, mCPVA will be completed 
Subjects will be followed up at 3, 6, 12 months.

Devices used:	
 - EnSite™ Velocity™ mapping system (CE marked) - Inquiry™ AFocusII™ diagnostic catheter (CE marked) - EnSite Velocity Research Platform consisting of: 
 o EnSite Velocity Research Display Workstation (CE marked) o EnSite Velocity Research Switch (OEM CE marked) o EnSite Velocity Research software (not CE marked) - Any commercially available Radiofrequency (RF) ablation system - Any commercially available irrigated tip RF ablation catheter (minimum 4 electrodes) - Any CE-marked EP diagnostic catheter (minimum 4 electrodes)
Study Population	Patients with persistent AF scheduled to undergo first or second time catheter ablation with approved standard indication by ESC/EHRA Guidelines

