Inclusion/Exclusion Criteria	
Inclusion Criteria
 
 1. Age between 18 and 85 years 2. Persistent AF 3. Ability to provide informed consent for study participation and be willing and able to comply with study evaluations and follow-up schedule

Clinical Investigational Plan Synopsis

	
Exclusion Criteria
 
1. Two or more previous AF ablations2. Secondary AF3. Hyperthyroidism4. Left ventricular ejection fraction <30%5. NYHA functional class IV6. Left atrial area > 35 cm²7. Uncorrected severe valvular heart disease8. Contraindication to anticoagulation9. Presence of left atrial thrombus10. Recent (<6 Months) myocardial Infarction or unstable angina or coronary artery by-pass11. Thoracic surgery for congenital, valvular or aortic disease12. History of cerebrovascular accidents13. Pregnancy14. Significant comorbidities such as cancer, severe renal insufficiency requiring hemodialysis, severe obstructive lung disease, cirrhosis, with a life expectancy less than 2 years
Data Collection	
- Pre-procedure: Data collection per standard clinical practice for patients undergoing AF ablation- During-procedure: EnSite Velocity Study Backup DVDs, including 3D geometry of LA, contact maps collected by AFocus II catheter, electrograms, RF lesion locations, marker locations, electrode locations, user annotations, events of acute AF termination or significant CL slowing 
Post-procedure: AF recurrence documented by ILR or TT ECG monitoring

Clinical Investigational Plan Synopsis

1. Study Flow Chart

Clinical Investigational Plan Synopsis

2. Statistical analysis

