In subjects with persistent AF, it is possible to demonstrate a one-year clinical difference among the two therapies with a significance level of 0.5 and a power of 0.80 using a Log-rank test in 38 subjects per group, estimated success of 50% and 80% in the control arm and mapping arm, respectively. The expected difference is based on extensive experience of the operators. Considering 5% drop-out rates, thus a total of 80 subjects will be included and assigned to either treatment group according to a randomization schedule stratified by the previous ablation procedures (none and one previous ablation procedure). Categorical and continuous variables are expressed as absolute and relative frequencies or as mean \pm SD or median (interquartile range [IQR]) as appropriate. Comparisons of continuous variables were done with a Student t-test or the Mann-Whitney U test as appropriate and binomial variables with chi-square or Fisher test. Long-term outcome was assessed, after a single ablation procedure, by Kaplan-Meier method and compared using the log rank test. A 2-tailed probability value of ≤ 0.05 was deemed significant. Statistical analyses were conducted using SPSS (SPSS v22, USA).

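### The primary log-rank test ignores the randomization stratum and baseline left atrial area, forgoing a modest, low-cost gain in power and protection against chance imbalance

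*Combined protocol and SAP*

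**What the plan says.** Section 2 (Statistical analysis) plans Kaplan-Meier estimation of long-term outcome after a single procedure, with the arms "compared using the log rank test". It names no stratification, covariate, hazard ratio or confidence interval. The same paragraph stratifies the randomization schedule by previous ablation, none versus one.

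The sample size rests on the same test: "a power of 0.80 using a Log-rank test in 38 subjects per group", with "estimated success of 50% and 80% in the control arm and mapping arm, respectively". The total follows from the loss allowance: "Considering 5% drop-out rates, thus a total of 80 subjects will be included".

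In the synopsis table, exclusion criterion 6 is "Left atrial area > 35" (in cm²). The Data Collection row says only that pre-procedure data follow standard clinical practice. It does not list left atrial area as a recorded item.

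**The concern.** A factor important enough to stratify randomization would normally be carried into the primary analysis. Here the log-rank test is not described as stratified. A further baseline value, left atrial area, must be checked in every patient before entry and is then not used.

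With about 40 patients per arm, chance differences between arms in a baseline variable are not rare. If that variable predicts recurrence, an unadjusted comparison carries the difference straight into the result. At stake are some power and some robustness of a single small trial's primary result. The plan also promises no effect estimate with an interval, which the model proposed below would supply.

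**Working it through.** **Inputs from the plan.** Success 50% versus 80%; 38 per group; 5% drop-out; 80 in total; 1:1 allocation; power 0.80; "A 2-tailed probability value of ≤ 0.05 was deemed significant". The sample-size sentence gives the significance level as 0.5. Taken literally, that needs only about 11 to 13 per group (17 with continuity correction), so 38 was evidently computed at two-sided 0.05, which is used here.

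**Reproducing the plan's figure.**
- Hazard ratio under proportional hazards: ln(0.8)/ln(0.5) = 0.322.
- Schoenfeld events: 4 × (1.960 + 0.842)² / (ln 0.322)² = 24.4, so 25.
- Mean event probability: (0.50 + 0.20)/2 = 0.35. Then 25/0.35 = 71.4, so 72 patients, 36 per group.
- Two-proportion formula: 39 per group. Freedman's formula is more demanding: 30 events, 43 per group.
- Loss: 76/0.95 = 80.

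The stated 38 lies between the Schoenfeld and two-proportion results. With 76 × 0.35 = 26.6 expected events, Schoenfeld power is 83% and Freedman power 75%. Simulated log-rank power, with 80 patients and 5% loss, is 81 to 82%. The planned test therefore delivers about what the plan says.

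**Effect of adjustment on power.** The documents give no relation between left atrial area and recurrence, so its hazard ratio (HR) per standard deviation (SD) is an assumption shown as a range. Times are exponential, the covariate is standard normal, and marginal success is held at 50% and 80%. Entries are power, log-rank / adjusted (%).

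| Assumed HR per SD | One covariate, no strata; 38 per arm; likelihood-ratio test | One covariate, no strata; 40 per arm, 5% loss; score test | Stratified Cox plus covariate; 40 per arm, 5% loss; likelihood-ratio test |
|---|---|---|---|
| 1.0 | 80.1 / 79.9 | 81.2 / 81.0 | 81.6 / 81.4 |
| 1.5 | 80.4 / 83.1 | 82.1 / 84.2 | 82.2 / 84.4 |
| 2.0 | 81.9 / 88.0 | 82.3 / 87.8 | 82.9 / 89.4 |
| 2.5 | not run | 81.3 / 91.6 | not run |

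The columns used 5,000, 2,500 and 2,000 trials per setting. The last column is the model proposed below and assumes that 30% have had a previous ablation. A separate simulation of that model gave 0.82 versus 0.82 for log-rank at HR 1.0, 0.83–0.85 versus 0.82–0.83 at 1.5, and 0.89 versus 0.84 at 2.0. Simulation error is just under 1 point for the 2,000- and 2,500-trial runs. Type I error was 4 to 6% for every test; for the stratified model in the table it was 0.053, 0.047 and 0.052.

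**Where the gain comes from.** Median standard error of the log HR, unadjusted to adjusted: 0.427 to 0.430 at HR 1.0, 0.429 to 0.433 at 1.5, and 0.429 to 0.443 at 2.5. It does not fall. The median log HR moves from −1.137 to −1.202 at 1.5 and from −1.160 to −1.382 at 2.5. At 2.5 the ratio of the two medians rises from 1.160/0.429 = 2.70 to 1.382/0.443 = 3.12. The adjusted model targets a conditional hazard ratio that lies further from 1.

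**Chance imbalance.** With 40 per arm, the difference in standardized covariate means has SD √(2/40) = 0.224. A difference beyond 0.3 SD in either direction is 0.3/0.224 = 1.34 SDs out, which happens in about 18% of trials. When it went against the mapping arm (about half of those trials), simulated power was about 0.68 for log-rank and 0.82 for the stratified adjusted model at HR 1.5, and about 0.61 and 0.88 at HR 2.0. Under the null at HR 2.0, log-rank rejected in about 0.096 of the imbalanced trials and the adjusted model in 0.042; at 1.5 the figures were 0.060 and 0.040. These subsets hold only a few hundred trials or fewer, so the figures are approximate.

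**The case against.** The strongest case is that this is preference. The log-rank test is valid, it matches the sample-size basis, and randomization protects its type I error. The document is a synopsis with a stated feasibility purpose. No passage links left atrial area to recurrence. Ejection fraction, NYHA class and age must also be known for eligibility, and nothing in the documents singles out left atrial area. Excluding areas above 35 cm² narrows its spread, which points to the lower end of the power range. All of that stands, and it is why the point is minor.

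The worry that splitting about 27 events across two strata would cost power is not borne out: with a useless covariate, the stratified model had 81.4% power against 81.6% for log-rank.

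Three stronger readings are tempting and are not supported:
- A reader might infer that the trial is underpowered or its test biased. The stated sample size reproduces and the test holds its level.
- A reader might infer that precision is being given away for free. The standard error of the log HR does not shrink, and the value must be captured as a data item, which the Data Collection row does not promise.
- A reader might infer that the 35 cm² limit shows the sponsor regards the area as prognostic. The list gives no rationale and also contains plain safety exclusions, such as left atrial thrombus.

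**Conclusion.** The point holds as a minor, optional improvement. The primary comparison is described as neither stratified by the factor used in randomization nor adjusted for a baseline value that every patient must have assessed. Using both costs essentially nothing if left atrial area is uninformative, and gains about 2 points of power at an assumed HR per SD of 1.5 and about 5 to 6 points at 2.0. The benefit is larger in the roughly one trial in five with a covariate imbalance beyond 0.3 SD, provided the covariate is prognostic.

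These sizes rest on proportional hazards, a roughly normal covariate, an assumed 30% with a previous ablation, and a prognostic strength that the documents do not give. The case for following the randomization stratum does not depend on that strength; the case for left atrial area does.

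**What to change.** In section 2, pre-specify the primary comparison as a Cox model for time to first primary-endpoint failure. Stratify it by previous ablation (none or one), with treatment and continuous baseline left atrial area as the only covariates. Test treatment by likelihood ratio at two-sided 0.05 and report the hazard ratio with 95% CI. The likelihood-ratio test is preferable to the Wald test, which was about 1 point less powerful than the adjusted score test in the simulations (for example 82.9% against 84.2% at HR 1.5). Keep the Kaplan-Meier curves, and report a log-rank test stratified by previous ablation as supportive. Add left atrial area, measured at screening by a stated method, to the data collected.

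The cost is one or two sentences, one extra model and one recorded value. Two downsides should be acknowledged in the text: the model relies on proportional hazards, and its hazard ratio is conditional on the covariate and stratum. If the sponsor prefers not to adjust for left atrial area, stratifying the log-rank test by previous ablation is the minimum change.
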